Investigational Therapy:	The screening period, up to 7 days for each patient, will be used to assess eligibility. Patients who are eligible will be allowed to participate. Those patients will be randomized to one of two groups: 1) placebo (saline solution) 2) HB-adMSCs. All patients will receive standard of care. Any placebo or HB-adMSC treatment will be in addition to standard care appropriate for their condition. After the study is finished the investigators should know whether or not HB-adMSCs are an effective treatment for

	COVID-19 and whether or not it is safe to give this medication to patients with COVID-19 infection. To ensure that the drug is safe, a Medical Monitor and DSMB will oversee the entire study. Laboratory data, including complete blood counts, serum chemistry and adverse events will be reviewed.
Treatment Duration:	The approximate maximum duration of treatment for each patient is 10 days (Day 0 through 10), and the approximate duration of the study is 28 days.
Criteria for Evaluation:	
Safety: Safety is assessed by primary and secondary endpoints. Primary safety endpoints include incidence of adverse and serious adverse events. Secondary safety endpoints include incidence of specific adverse events including serious infections, infusion-related reactions, hepatotoxicity, heart failure, and cytopenias. Clinically significant changes in laboratory values, vital signs, weight, and physical examination results will also be measured.
 
Efficacy: Clinical efficacy is assessed by primary and secondary endpoints. Primary endpoints include the change from baseline in inflammatory markers (IL-6, IL-10, TNF-alpha, C Reactive protein), change from baseline oxygenation, and time to return to room air (RTRA). Secondary endpoints include change from baseline of chest x-ray, change from baseline of CT scan, change from baseline of clinical laboratory values, adverse and serious adverse events, change in exploratory markers (D-dimer, myoglobin, troponin, creatinine kinase, serum ferritin, CD3CD56, CD4/CD8, VEGF), time to negative PCR results, and change in ordinal scale.

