
The drug for this submission is Hope Biosciences' allogeneic, adipose-derived culture-expanded mesenchymal stem cells (HB-adMSCs) to treat COVID-19. We hypothesize that the immunomodulatory properties of MSCs will inhibit cell-mediated immune inflammatory responses and MSC endogenous regenerative properties will reduce pathological changes of lung associated with COVID-19. The population we are proposing to treat are suspected to be positive

for COVID-19, which will be confirmed by testing during the trial. We have preclinical safety and efficacy data, as well as clinical evidence of the safety of HB-adMSCs in patients in ongoing phase I/IIa clinical trials for Rheumatoid Arthritis (NCT03691909), Traumatic Brain Injury and/or Hypoxic-Ischemic Encephalopathy (NCT04063215), and Alzheimer's Disease (NCT04228666), as well as individual expanded access for Parkinson's Disease (NCT04064983), Spinal Cord Injury (NCT04064957 and NCT03925649), and Cerebral Palsy (NCT04029896). We have experience with an individual expanded access for Pancreatic Cancer (NCT04087889) who received allogeneic HB-adMSCs, as well. All treatments have been well-tolerated, with no severe adverse events related to the study drug.

Study Objectives and Endpoints

Study Objectives

Primary:

- To investigate the safety and efficacy of HB-adMSCs as a treatment for patients suspected to have COVID-19.

Secondary:

- To investigate the safety and efficacy of HB-adMSCs in improving clinical status of patients suspected to have COVID-19 infection.

Study Endpoints

Primary:

- change from baseline in inflammatory markers (TNF-alpha, IL-10, IL-6, C-Reactive protein)
- change from baseline oxygenation
- Time to return to room air (RTRA)

Secondary:

- Change in clinical laboratories
- Change from baseline Chest X-ray
- Change from baseline CT scan
- Change from baseline in exploratory markers (D-dimer, myoglobin, troponin, creatinine kinase, serum ferritin, CD3CD56, CD4/CD8, VEGF)
- Time to negative PCR test results
- Change from baseline in the 7-point ordinal scale
- Cumulative incidence of serious adverse events (SAEs) or adverse events (AEs)

Investigational Plan

This Phase II, randomized, placebo-controlled, double-blinded, trial assesses efficacy in a population of hospitalized patients to evaluate efficacy of HB-adMSCs to treat Coronavirus Disease. It is designed to be conducted in 2 arms:

Consenting patients will be randomly assigned to one of two arms:

Arm 1 (HB-adMSCs) (n=60)

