Patients will receive four intravenous infusions of 100 million HB-adMSCs throughout the entire duration of the study.

Arm 2 (placebo) (n=40)

Patients will receive four intravenous infusions of placebo (saline solution) throughout the entire duration of the study.

Safety assessments will be ongoing. Safety tests will include EKG, Complete Blood Count with differential, Complete Metabolic Profile (to include renal function and hepatic function) and Coagulation Panel screening for hepatotoxicity, cytopenias, renal failure or alterations in the coagulation cascade that might entail a safety concern for the individual. Efficacy will be measured by change from baseline in inflammatory markers (IL-6, CRP, IL-10, TNF-alpha), change from baseline in oxygenation, and time to receive negative PCR test result, change from baseline in exploratory markers (D-dimer, myoglobin, troponin, creatinine kinase, serum ferritin, CD3CD56, CD4/CD8, VEGF), time to return to room air (RTRA), change from baseline chest x-ray, change from baseline CT scan, and change from baseline in 7-point ordinal scale.

Selection and Withdrawal of Patients

Inclusion Criteria

1. Men, and women, over 18 years of age inclusively.
2. Suspected COVID-19 infection
3. Provides consent or consent is given by their legally authorized representative (LAR)
4. Agrees to the collection of venous blood per protocol.

Exclusion Criteria:

1. Pregnancy, lactation and those who are not pregnant but do not take effective contraceptive measures, in women of childbearing age.
2. Patients who have participated or are participating in a clinical trial of an experimental vaccine for SARS-CoV-2 or coronavirus during the study or within 30 days.
3. Inability to provide informed consent or to comply with test requirements.

4. Any medical disease or condition that, in the opinion of the site Principal Investigator or sub-investigator, precludes study participation. Including acute, subacute, intermittent or chronic medical disease or condition that would place the subject at an unacceptable risk of injury, render the subject unable to meet the requirements of the protocol, or may interfere with the evaluation of responses or the subject's successful completion of this trial.

Withdrawal, Removal, and Replacement of Patients

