- Hands must be washed with soap and water for at least 20 seconds, if soap and running water are unavailable, an alcohol-based hand rub with at least 60% alcohol will suffice this action. Always wash hands that are visibly soiled.
- Avoid touching their eyes, nose or mouth.
- Healthcare workers will wear:
 - o Disposable Gowns
 - o Gloves
 - o Disposable N95 masks.
 - o Eye/face protection (e.g., goggles, face shield)
- Surfaces where subjects have been in contact will be disinfected 70% Isopropyl Alcohol.

Pre-infusion Medication

Prior to infusion, medications will be given to the participant as a precaution. Because the drug for this study is an allogeneic product, an allergy medication such as Loratadine (10mg), will be administered. The participant will be closely monitored for any signs of allergic reaction during the infusion and during the post-infusion monitoring period. No reactions are expected.

Potential Benefits

Subjects may benefit from their participation in the study by experiencing an overall feeling of well-being. Subjects enrolled in the study will be contributing to the advancement of science and to future investigations regarding stem cells and possible therapeutic applications, including treatment of respiratory diseases, specifically COVID-19.

Statistical Analysis

Determination of Sample Size

Sample size calculation was determined based upon the anticipated demand for treatment.

Null hypothesis- Efficacy

Treatment with HB-adMSCs does not cause changes in primary and secondary endpoints (listed below) for suspected Corona Virus Disease.

Alternative hypothesis-Efficacy

The alternative hypothesis for this study is that HB-adMSC treatment does result in changes from baseline values of primary and secondary endpoints in patients with suspected Corona Virus Disease.

Null hypothesis-Safety

Treatment with HB-adMSCs results in adverse or serious adverse events and/or detrimental changes in laboratory values, vital signs, weight, X-rays, EKG, or physical examination determined to be related to the study drug.

Alternative hypothesis-Safety

HB-adMSC treatment for COVID-19 does not result in adverse or serious adverse events and/or detrimental changes in laboratory values, vital signs, weight, X-rays, EKG, or physical examination determined to be related to the study drug.

Endpoints

The endpoints measured in this study are safety and clinical efficacy.

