40-49 years		
50-59 years		
60-69 years		
70-79 years		
80-89 years		
90-99 years		
100-109 years		
Total	100	100
		%

Safety Analysis

The number, type, and description of all AEs and SAEs will be recorded and reported.

Efficacy Analysis

- change from baseline in oxygenation will be recorded and compared between placebo and treatment group; higher mean oxygen saturation in treatment group compared to placebo would indicate HB-adMSCs are effective in improving oxygenation compared to placebo
- change from baseline in inflammatory markers will be compared between placebo and treatment group; decreased values of D-dimer, IL-6, and CRP in treatment group compared to placebo group would indicate HB-adMSCs are effective in decreasing inflammation
- Time to clear PCR test; a decreased duration of time to achieve a clear PCR test in treatment group compared to placebo group would indicate that HB-adMSCs are effective in decreasing the length of time a subject is contagious
- Time to return to room air (RTRA); a decreased duration of time to achieve a return to room air (no supplementation) in treatment group compared to placebo group would indicate that HB-adMSCs are effective in decreasing the length of time a subject requires respiratory assistance or supplementation.

Interim Analysis

Interim analysis of all safety and efficacy data may be performed at any time deemed appropriate by the Sponsor. Data will be analyzed for internal informational purposes, reports, presentations, and manuscripts.

Study Management

Institutional Review Board and Informed Consent

Hope Biosciences Stem Cell Research Foundation is required to obtain IRB oversight of the research study. The IRB must be provided with Hope Biosciences Stem Cell Research Foundation -approved study protocol. Performance of the study may not begin until written evidence of IRB approval has been provided to Hope Biosciences Stem Cell Research Foundation. The conduct and performance of this study will be in accordance with applicable Hope Biosciences Stem Cell Research Foundation and Investigator responsibilities as described in Title 21 CFR 312, subpart D and other Good Clinical Practice guidance.

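### The protocol's safety alternative requires no drug-related event at all, which no sample can establish; safety should be estimated, on the Safety analysis set

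*Protocol*

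**What the plan says.** The protocol's Statistical Analysis section gives a pair of safety hypotheses. The null is that "Treatment with HB-adMSCs results in adverse or serious adverse events and/or detrimental changes in laboratory values, vital signs, weight, X-rays, EKG, or physical examination" that are "determined to be related to the study drug". The alternative is the reverse: "HB-adMSC treatment for COVID-19 does not result in adverse or serious adverse events and/or detrimental changes in laboratory values", with the same list and the same relatedness qualifier.

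The Synopsis (Investigational Therapy) says that at the end of the study the investigators should know "whether or not it is safe to give this medication to patients with COVID-19 infection". The protocol's Safety Analysis paragraph is descriptive: "The number, type, and description of all AEs and SAEs will be recorded and reported".

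The SAP treats safety in four places:
- Section 2.4 (Statistical Hypotheses) restates the efficacy pair and has no safety hypothesis.
- Section 7.2.1 lists cumulative incidence of AEs and SAEs as a secondary endpoint. Section 7.2.4.2 models AE/SAE occurrence and AE severity as dichotomous outcomes, and attribution to study drug as counts.
- Section 5.7 promises estimated treatment differences with 95% credible intervals and posterior probabilities for every endpoint analysed statistically. It also places all safety evaluations on the Safety analysis set.
- Section 7.2.3 places the secondary efficacy analyses on the Efficacy analysis set unless otherwise specified. Section 4 defines that set as randomized patients who received all four infusions.

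**The concern.** The alternative is a claim that the related-event rate is exactly zero. It covers AEs of any intensity, and the protocol's intensity scale starts at mild. It also covers laboratory values, vital signs, weight, imaging, EKG and physical examination. There is no acceptable rate and no reference to placebo. Nor does the text say whether an event graded as possibly related, a category defined under Causal Relationship of Adverse Events, counts as related.

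The favourable conclusion is therefore out of reach however clean the data are, while one related event is enough to contradict it. The Synopsis nevertheless leads the reader to expect an answer on safety, and neither document says what evidence would supply one. What is at stake is how a clean or nearly clean safety table is described in the report: as a finding of no drug effect, or as a rate with a stated upper limit.

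**Working it through.** **Inputs**
- Treated patients: 60, and placebo patients: 40 (protocol, Investigational Plan). This agrees with the 3:2 ratio in SAP section 2.2: 100 × 3/5 = 60.
- Safety population: at least one infusion (protocol, Analysis Population; SAP section 4), so up to 60 treated. As a low-end sensitivity value I apply the Synopsis's 15% drop-out: 60 × 0.85 = 51.
- Related-event rate, safety margin and safety power: none given. The rates below are assumptions.

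There is no safety calculation in the plan to reproduce. The protocol says the sample size was set by expected demand.

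**Step 1. What the best possible result excludes.** With zero events in n patients, the upper limit p solves (1 − p)^n = a, so p = 1 − a^(1/n).
- n = 60, one-sided 95% (a = 0.05): 1 − 0.05^(1/60) = 4.9%.
- n = 60, two-sided 95% (a = 0.025): 1 − 0.025^(1/60) = 6.0%.
- n = 51: 5.7% and 7.0%.

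The SAP's Beta(1,1) prior for proportions (section 7.1.4.1) gives nearly the same answer. The posterior after 0/60 is Beta(1,61), with upper limits 1 − 0.05^(1/61) = 4.8% and 1 − 0.025^(1/61) = 5.9%. The limit comes from the sample size, not from the school of inference.

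**Step 2. Whether a larger sample would help.** Zero events exclude a rate p (one-sided 95%) once n ≥ ln(0.05)/ln(1 − p). That is 59 patients for 5%, 149 for 2%, 299 for 1% and 2,995 for 0.1%. No n excludes every rate above zero.

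**Step 3. How often 60 patients give each picture.** P(no event) = (1 − p)^60.

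| Assumed true related-event rate | Zero events in 60 | At least one |
|---|---|---|
| 0.5% | 74.0% | 26.0% |
| 1% | 54.7% | 45.3% |
| 2% | 29.8% | 70.2% |
| 5% | 4.6% | 95.4% |

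At 1%, a clean table is more likely than not although the alternative is false. At 2%, the alternative is contradicted about 70% of the time.

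**Step 4. Which patients the between-arm AE models use.** SAP section 5.7 points to the Safety set. Section 7.2.3, which governs the section containing the models, points to the four-infusion set. The protocol lets an infusion be withheld for an ongoing AE (Infusion Schedule) and lists safety reasons for discontinuing treatment (Withdrawal, Removal, and Replacement of Patients). On the default, patients who missed an infusion because of harm drop out of the AE comparison.

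**The case against.** The strongest reply is that the safety pair has no operative role. The SAP defines the analyses for the study report, and section 2.4 leaves the pair out. Safety decisions during the trial rest on the stopping rules and scheduled DSMB reviews, which do not refer to these hypotheses. The limits in Step 1 apply to any 60-patient arm, and deleting the hypotheses changes none of them.

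Much of this stands, and it rules out three stronger readings that a reader might infer:
- *That zero related events will be reported as safe and one trivial event as not safe.* Neither document contains that decision rule.
- *That the safety analysis consists of counts only and ignores placebo.* This fits the protocol's Safety Analysis paragraph and SAP section 8.1, but not the whole plan. SAP sections 5.7, 7.2.1 and 7.2.4.2 together commit to between-arm AE/SAE models with 95% credible intervals.
- *That no safety conclusion of any kind is possible.* Only the favourable one is unreachable. If an event is determined to be drug-related, retaining the null is correct as the null is worded.

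The reply does not dispose of the point. The SAP drops the safety pair without replacing it, and neither document gives a margin, acceptable rate or posterior-probability threshold that would support the Synopsis statement. The models that could carry the safety conclusion are assigned to two different populations.

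**Conclusion.** The point holds as a fault in what the plan says it can conclude about safety, not as a fault in a test that will be run. The favourable hypothesis cannot be established. The best result available, 0 of 60, is compatible with a related-event rate of up to 4.9% (one-sided 95%) or 6.0% (two-sided 95%), and up to 5.7% or 7.0% if only 51 treated patients are analysed. These limits assume independent patients and a per-patient event proportion. The probabilities of a clean table, 55% at a 1% rate and 30% at 2%, rest on assumed rates. The population conflict for the AE models is a matter of text and needs no assumption.

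Nothing here suggests that the product is unsafe or that safety oversight during the trial is deficient.

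**What to change.** 1. Delete both safety hypotheses from the protocol's Statistical Analysis section. State there, and in SAP section 2.4, that safety is estimated and not tested.
2. Name the estimates: the HB-adMSC versus placebo differences for any AE and any SAE, with 95% credible intervals, from the models already planned in SAP section 7.2.4.2.
3. State in section 7.2.3 or 7.2.4.2 that those models use the Safety analysis set, so that they agree with section 5.7.
4. Add the upper bound for related SAEs in the HB-adMSC arm and label its type. For zero of 60, it excludes rates above about 5% (one-sided 95%) or about 6% (two-sided 95%). Recalculate it for the number actually treated, and state whether possibly related events count.
5. In the Synopsis, replace the promise to know whether the product is safe with a statement that the study will give the rate and range of adverse events compatible with the data.

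No visit, treatment or data collection changes. The SAP is marked version 1.0, Draft, so its part can still be made. The cost is the rewording, one extra interval per table, and a weaker safety claim.

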Appendix 1: Clinical Criteria for Diagnosing Anaphylaxis

Anaphylaxis is defined as a serious allergic reaction that is rapid in onset and may cause death. The following criteria were outlined by Sampson et al from the Second Symposium on the Definition and Management of Anaphylaxis (a 2005 meeting of the National Institute of Allergy and Infectious Disease and Food Allergy and Anaphylaxis Network).

Anaphylaxis is highly likely when any 1 of the following 3 criteria are met:

1. Acute onset of an illness (minutes to several hours) with involvement of the skin, mucosal tissue, or both (e.g., generalized hives, pruritus or flushing, swollen lips-tongue-uvula) AND at least 1 of the following:
 - a. Respiratory compromise (e.g., dyspnea, wheeze-bronchospasm, stridor, reduced peak expiratory flow, hypoxemia)
 - b. Reduced blood pressure (BP) or associated symptoms of end-organ dysfunction (e.g., hypotonia [collapse], syncope, incontinence)
2. Two or more of the following that occur rapidly after exposure to a likely allergen for that patient (minutes to several hours):
 - a. Involvement of the skin-mucosal tissue (e.g., generalized hives, itch-flush, swollen lips-tongue-uvula)
 - b. Respiratory compromise (e.g., dyspnea, wheeze-bronchospasm, stridor, reduced peak expiratory flow, hypoxemia)
 - c. Reduced BP or associated symptoms of end-organ dysfunction (e.g., hypotonia [collapse], syncope, incontinence)
 - d. Persistent gastrointestinal symptoms (e.g., crampy abdominal pain, vomiting)
3. Reduced BP after exposure to known allergen for that patient (minutes to several hours):
 - a. Infants and children: low systolic BP (age-specific) or greater than 30% decrease in systolic BP. Low systolic BP for children is defined as less than 70 mmHg from 1 month to 1 year, less than (70 mmHg + [2 x age]) from 1 to 10 years, and less than 90 mmHg from 11 to 17 years.
 - b. Adults: systolic BP of less than 90 mmHg or greater than 30% decrease from that person's baseline

References

1. Lopes-Pacheco, M., et al., *Current understanding of the therapeutic benefits of mesenchymal stem cells in acute respiratory distress syndrome*. Cell biology and toxicology, 2019: p. 1-20.
2. Sun, P., et al., *Understanding of COVID-19 based on current evidence [published online ahead of print, 2020 Feb 25]*. Journal of Medical Virology, 2020.
3. *Clinical Pharmacology*. 2019, Elsevier: Tampa, FL.

## 1. INTRODUCTION

The purpose of this statistical analysis plan (SAP) is to describe the analyses to be included in the Clinical Study Report for Protocol HBCOVID03:

## 2. SUMMARY OF KEY PROTOCOL INFORMATION

### 2.1. Study Objective(s) and Endpoint(s)

Objectives	Endpoints
Primary Objective	Primary Endpoint

To investigate the safety and efficacy of HB-adMSCs in the treatment of patients with COVID-19 by decreasing inflammation, improving oxygenation, and decreasing time to return to room air (RTRA)

	

Change from baseline in inflammatory markers (TNF-alpha, IL-10, IL-6, C-Reactive protein)

Change from baseline oxygenation

Time to return to room air (RTRA) and proportion of patients with room air status

Secondary Objectives	Secondary Endpoints

Objectives	Endpoints

• To investigate the safety and efficacy of HB-adMSCs in improving clinical status of patients suspected to have COVID-19).

	

• Change in clinical laboratories

• Change from baseline Chest X-ray

• Change from baseline CT scan

• Change from baseline in exploratory markers (D-dimer, myoglobin, troponin, creatinine kinase, serum ferritin, CD3CD56, CD4/CD8, VEGF)

• Time to negative PCR test results

• Change from baseline in the 7-point ordinal scale

• Cumulative incidence of serious adverse events (SAEs) or adverse events (AEs)

## 2.2. Study Design

Overview of Study Design and Key Features	
Randomized, double-blind, placebo-controlled, parallel group study	
Design Features	

• Randomized, double-blind, Placebo controlled study.

• 100 Subjects

• 2 Treatment groups

▪ Group 1 → HB- adMSCs

▪ Group 2 → Placebo

• Duration of treatment: up to 7 days, and overall study includes screening (up to 7 weeks prior to randomisation), and 4 treatment visits after randomisation scheduled at Infusion 1 (Day 0), Infusion 2 (Day 3), Infusion 3 (Day 7), and Infusion 4 (Day 10). Follow-up at day 28 (EOS).

Dosing	

• HB- adMSCs (Hope Biosciences adipose derived mesenchymal stem cells) is to be administered as an IV infusion with a dose of 100 million cells

• Placebo is to be administered as an IV infusion. Contains Saline solution 0.9%

Treatment Assignment	

• Participants will be randomised 3:2 to receive HB-adMSCs active treatment or Placebo.

